9	Study Assessments and Procedures	11
9.1	Schedule of Activities	11
9.2	Detailed Study Assessments	12

9.2.1	Screening.....	12
9.2.2	Visit before fertility treatment	12
9.2.3	Visit after fertility treatment	12
9.3	Assessment types	12
9.3.1	IBS symptoms.....	12
9.3.2	Gastrointestinal symptoms	13
9.3.3	Depression levels	13
9.3.4	Anxiety levels.....	13
10	Data Collection and Management.....	14
10.1	Monitoring	14
10.2	Data Collection	14
10.3	Data collection from patient file	14
10.4	Database Management and Quality Control	14
10.5	Statistical Considerations and Data Analysis	15
11	Ethical Considerations	16
11.1	Ethical Conduct of the Study	16
11.1.1	Declaration of Helsinki.....	16
11.1.2	Ethics Committee	16
11.2	Recruitment and Informed Consent	16
11.3	Study Data Protection	16
11.4	Subject Identification	16
12	Insurance.....	16
14	Finance and Conflict of Interest Statement	17
15	References	18
16	Appendices.....	20

1 Sponsor/Coordinating Investigator Information

Sponsor:	VUB
Principal Investigator:	[name]. [name]
Sub-investigator(s):	[name] [name], [name]. [name] , [name]
Statistician:	[name]
Study Coordinator:	[name]
Study site(s) :	BIVF , UZ Brussel

2 List of Abbreviations

IBS	Irritable Bowel Syndrome
IBS-SSS	Irritable Bowel Syndrome- Symptom Severity Scale
COC	Cumulus-oocyte complex
COS	Controlled ovarian stimulation
GAD-7	Generalized Anxiety Disorder 7-item
GI	Gastrointestinal
GPA	Gravida, para and abortus
GSRS	Gastrointestinal Symptom Rating Scale
ICF	Informed Consent Form
IVF	In Vitro Fertilization
PCOS	Polycystic Ovarian Syndrome
PHQ-9	Patient Health Questionnaire 9
PPOS	Progestin-Primed Ovarian Stimulation
US	Ultrasound
VUB	Vrije Universiteit Brussel

3 Protocol Version History

Version N°	Version Date	Summary of changes
1	01/10/2025	
2	10/11/2025	Response to questions EC
3	03/02/2026	Response to questions EC

4 Trial Registration/Protocol Summary

Information	
Objectives:	The objective is to study IBS (Irritable bowel syndrome) symptoms in women who undergo controlled ovarian stimulation and oocyte retrieval, which are the cornerstones of fertility treatment. Two groups will be studied: women with PCOS (Polycystic Ovarian syndrome) and women who undergo elective oocyte cryopreservation (social freezing).
Study population:	Nulliparous women with a diagnosis of PCOS who are eligible for IVF (in vitro fertilization) treatment with freeze-only strategy (i.e. deferred embryo transfer). Nulliparous women who embark on elective oocyte

	
cryopreservation. Both groups will receive PPOS (progestin-primed ovarian stimulation).

In- and exclusion criteria:	
Inclusion criteria PCOS group :
 
 - Diagnosis of PCOS according to the 2004 Rotterdam criteria - Initiating their first cycle of IVF treatment (PPOS and freeze only protocol) - Nulliparous - ≥ 18 years - Willing to participate in the study - Understanding Dutch, French or English 
Exclusion criteria PCOS group :
 
 - Known inflammatory bowel disorder - Known major intestinal bowel disorder - Known systemic or auto-immune disorder with implication for the GI system - History of abdominal surgery (appendectomy and cholecystectomy allowed if >6 months earlier) - History of gastro-enteritis in the past 6 weeks - Previous IVF treatment cycles 
Inclusion criteria social freezing group:
 
 - Initiating their first ovarian stimulation protocol for elective oocyte cryopreservation (PPOS and freeze only protocol) - Nulliparous - ≥ 18 years - Willing to participate in the study - Understanding Dutch, French or English 
Exclusion criteria social freezing group:
 
 - Diagnosis of PCOS - Known inflammatory bowel disorder - Known major intestinal bowel disorder - Known systemic or auto-immune disorder with implication for the GI system - History of abdominal surgery (appendectomy and cholecystectomy allowed if >6 months earlier) - History of gastro-enteritis in the past 6 weeks
Factors of interest / Data to be collected:	
IBS diagnosis and symptom severity Gastrointestinal symptom severity Depression levels Anxiety levels
 
Factors to be collected before ovarian stimulation:
 
 • Demographics (length, weight) • The duration of infertility • Obstetrical history: GPA (Gravida, Para and abortus) • The ethnicity • For the study group: the type of PCOS 
Factors to be collected after oocyte pick-up:
 
 • The hormonal profile at start and end of ovarian stimulation • The number of follicles on the last ultrasound before pickup • The number of COC (Cumulus-oocyte complex) collected during pick-up


Endpoints:
	
The primary endpoint is to explore whether there is a difference between the IBS prevalence before and after ovarian stimulation.
 
The score on the Rome Criteria for IBS before and after ovarian stimulation will be compared.
 
The severity of IBS symptoms before and after the fertility treatment will be compared using the IBS-SSS (IBS- Symptom Severity Scale) questionnaire.
 
The prevalence of gastrointestinal symptoms before and after the fertility treatment will be compared using the GSRS (Gastrointestinal symptom rating scale) questionnaire.
 
The prevalence of anxiety levels before and after the fertility treatment will be compared using the GAD-7 (Generalized Anxiety Disorder 7-item) questionnaire.
 
The depression levels before and after the fertility treatment will be compared using the PHQ-9 (Patient Health Questionnaire 9).
 
The PCOS and social freezing group will each be divided in different subgroups based on the type of stimulation.
 
The IBS prevalence (with the Rome Criteria) and the IBS symptom severity (with the IBS-SSS) will be compared in these subgroups before and after ovarian stimulation.
 
The same will be done based on the number of treatments that were received before this treatment, the duration of -infertility, the number of previous pregnancies, the number of children, the ethnicity, the hormonal profile during COS (continuous ovarian stimulation).
 
The PCOS group will be divided in different subgroups based on the type of PCOS. . The IBS prevalence (with the Rome Criteria) and the IBS symptom severity (with the IBS-SSS) will be compared in these subgroups before and after the fertility treatment.


Target sample size:
	
Since there is no study that has explored the prevalence of IBS during a fertility treatment, there is not enough data to do a power analysis before starting this study. This study will be an explorative study with a PCOS group of 60 and social freezing group of 60. After the data has been collected, a power analysis will be done and the option of including more participants will be explored. In this case, we will submit an amendment to the ethical committee.
 
There are multiple studies that found a connection between IBS and infertility. Most of these studies are retrospective studies and are focused on male infertility. (1). A study in 2013 analyzed gastro-intestinal symptoms during IVF in infertile women. This study had 124 participants. (2) Since this study from 2013 is the most like our study, the aim for our target sample size is going to be similar, namely 120 participants.

5 Background and Rationale

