6.1 Primary Objective

The primary objective of this study is to investigate whether fertility treatment is associated with changes in the **prevalence** and **severity** of Irritable Bowel Syndrome (IBS) symptoms. Specifically, the study aims to:

1. Assess whether the **proportion of participants meeting IBS diagnostic criteria** (based on ROME III and IV) differs **before and after fertility treatment**.
2. Evaluate whether there is a **statistically significant change in IBS symptom severity** as measured by the **IBS Symptom Severity Score (IBS-SSS)** before and after treatment.

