6.1.1 Primary research hypotheses

H1.

The prevalence of participants meeting diagnostic criteria for Irritable Bowel Syndrome (IBS), as defined by the ROME III and ROME IV criteria, differs significantly before and after fertility treatment.

H2.

IBS symptom severity, as measured by the IBS Symptom Severity Score (IBS-SSS), changes significantly following fertility treatment compared with baseline.

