6.2.1 Secondary research hypotheses

H3.

Changes in depressive symptom levels are significantly associated with changes in IBS symptom severity in women undergoing fertility treatment.

H4.

Changes in anxiety levels are significantly associated with changes in IBS symptom severity in women undergoing fertility treatment.

H5.

Changes in IBS symptoms differ significantly according to the type of ovarian stimulation used during fertility treatment.

H6.

Changes in IBS symptoms differ significantly based on the number of fertility treatments received prior to the current treatment.

H7.

Changes in IBS symptoms differ significantly according to the duration of infertility.

H8.

The prevalence and/or change in IBS symptoms differ significantly across ethnic groups.

H9.

Among women with Polycystic Ovary Syndrome (PCOS), changes in IBS symptoms differ significantly according to PCOS phenotype.

H10.

Changes in IBS symptoms are significantly associated with the hormonal profile during controlled ovarian stimulation (COS).

H11.

Changes in IBS symptoms differ significantly according to the ovarian response assessed by ultrasound during COS.

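### The sample-size paragraph plans a power analysis on completed outcome data with optional extra enrolment, not limited to nuisance quantities and without error control, while the hypotheses are significance claims

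*Protocol*

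**What the plan says.** Everything on sample size is in the Target sample size entry of section 4. It says that "there is not enough data to do a power analysis before starting this study" and continues: "This study will be an explorative study with a PCOS group of 60 and social freezing group of 60". The total is taken by analogy with an earlier study of 124 participants: "the aim for our target sample size is going to be similar, namely 120 participants".

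The entry then looks ahead: "After the data has been collected, a power analysis will be done and the option of including more participants will be explored". The one safeguard is procedural: "In this case, we will submit an amendment to the ethical committee". No trigger, maximum size, choice of effect for the power calculation, or treatment of the first 120 women relative to added ones is stated. Section 10.5 (statistical considerations) does not mention an extension, and section 7.2 (date range) schedules none.

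The hypotheses are nevertheless framed as significance claims. Under H1 the prevalence of IBS "differs significantly before and after fertility treatment". The second primary aim in section 6.1 is a "statistically significant change in IBS symptom severity". The secondary hypotheses continue in the same style, for example H11: "Changes in IBS symptoms differ significantly according to the ovarian response assessed by ultrasound during COS". No significance level or sidedness appears anywhere in the protocol.

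**The concern.** The look is placed after the outcomes are known. If power is then computed at the observed effect, it is only the p-value in another form and adds no information. Low power of that kind reflects a small test statistic, so an extension decided on it is an extension decided on the result. If the pooled data are then tested as though the final size had been fixed from the start, the hypothesis has had a second chance at significance.

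A p-value obtained after such an extension could not be read at its nominal level. Because nothing about the extension is fixed, a reader could not work out the true level either. This is not a detail that a protocol would normally leave to an analysis plan: the protocol itself announces the data-dependent step and leaves its basis open.

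**Working it through.** **Stated figure.** 60 + 60 = 120 adds up. No level, power, effect size or standard deviation is given, so there is no sample-size calculation or type I error to reproduce.

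**Inputs**

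- From the protocol: first-stage size 120 (section 4).
- Assumed, because the protocol is silent: two-sided 5% (critical value 1.96), the trigger, the final size N, and an unadjusted re-test of the pooled data.

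**Observed power and the p-value.** Ignoring the far tail, power at the observed effect is Φ(|z| − 1.96).

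- At p = 0.05, |z| = 1.96 and the power is Φ(0) = 50%.
- Power of 80% needs |z| = 1.96 + 0.84 = 2.80, which is p of about 0.005.

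An 80% rule would therefore also extend studies with p between 0.005 and 0.05. Low observed power and non-significance are different triggers and are kept apart below.

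**Case A: test at 120, extend if not significant, re-test pooled data at 5%.** With Z1 at 120 and Z2 at N, the correlation is √(120/N) and the error is 1 − P(|Z1| < 1.96, |Z2| < 1.96).

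| Final N | Extension | Per-test error |
|---|---|---|
| 150 | 25% | 7.1% |
| 180 | 50% | 7.7% |
| 240 | 100% | 8.3% |
| 360 | 200% | 8.8% |
| 480 | 300% | 9.1% |

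**Case B: as A, but extended only when the first result is promising (N = 150 to 360).**

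- First p below 0.10: 5.6% to 6.1%.
- First p below 0.20: 6.5% to 6.9%.
- First p below 0.50: 7.1% to 7.9%.

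**Case C: stop if significant at 120, otherwise extend to the size giving 80% power at the observed effect, up to a cap.** The error is 7.7% (cap 180), 8.3% (240), 8.9% (360), 9.3% (480) and 10.1% (1200; 0.1005 before rounding).

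**Case D: no test at 120, extend if observed power is below 80%, one final test.** The error is 5.4% (cap 180), 5.8% (240), 6.5% (360), 6.8% (480) and 7.6% (1200).

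**H1 as a paired binary comparison.** Section 10.5 names no paired test, so McNemar is an assumption here. Case A with N = 240 was simulated (60,000 runs):

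| Discordant pairs | Asymptotic | Exact |
|---|---|---|
| 3% | 7.1% | 1.8% |
| 5% | 7.8% | 3.3% |
| 10% | 8.2% | 4.7% |
| 20% | 8.5% | 5.7% |

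The exact test starts well below 5% when discordant pairs are few (0.4% to 3.0% at 120), and that reserve absorbs most of the inflation.

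**Precision of the fixed size.** For the mean IBS-SSS change, the 95% half-width is 1.96/√n standard deviations of change: 1.96/√60 = 0.25 per group and 1.96/√120 = 0.18 overall. For the change in IBS prevalence with discordant fraction d, it is about 1.96 × √(d/n) when the true change is small. At n = 120 this gives 1.96 × √(0.03/120) = 3.1 percentage points for d = 3% and 1.96 × √(0.20/120) = 8.0 points for d = 20%. The values of d are assumptions.

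**The case against.** **The paragraph does not say that power will be computed at the observed effect.** Since it complains of missing data, it can equally mean that the collected standard deviation or discordance rate will be used for planning. Section 9.3.1 even offers a target, a 15% change in IBS-SSS score. This stands: the text is open, not demonstrably result-driven. It is also what the fix should close, because the harmful reading is equally allowed.

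**An extension is only to be explored, through an ethics amendment, and the study is called explorative.** An amendment is a place where a rule could be written, but it would be written after the outcomes are known and is not in itself an error control. The exploratory label lowers the weight of the point. It does not remove it while the hypotheses are claims of significance.

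**The analysis plan, which is not at hand, might adjust the level.** It might, and then this source of inflation disappears. The same is true if no extension takes place.

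**A reader might infer that all of H1 to H11 would run at 7% to 9%.** The documents do not support that. The level, the trigger, the size, the first test at 120 and the pooling are all assumptions. One power analysis would drive one decision, and a final test of a hypothesis unrelated to that trigger is not inflated by it. The figure needs each hypothesis to be tested at 120 and again later. For hypotheses tested in the models that section 10.5 selects by AIC, a 5% starting level is not assured even without an extension.

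**Conclusion.** The point holds in a limited form. The protocol commits to a power analysis on completed outcome data with possible further enrolment, does not restrict it to nuisance quantities and sets no error control, beside hypotheses worded as significance claims.

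Under an assumed two-sided 5% level, the per-test error is about 7% to 9% for test, extend if not significant and re-test, with extensions of 25% to 300%. Across the other readings it runs from about 5.4% to 10%. H1 under an exact McNemar test may stay near or below 5%, so the concern is clearest for the continuous IBS-SSS change. These are per-test rates, not a family-wise rate over the eleven hypotheses. The inflation depends on how the extension is carried out and is not fixed by the text. This is a cheap improvement rather than a defect that invalidates the study.

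**What to change.** Reword the Target sample size entry in section 4:

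- State that no power will be computed from the observed effect, and give the precision of 60 + 60 instead: half-widths of about 0.25 (per group) and 0.18 (overall) standard deviations of IBS-SSS change, with the matching figure for prevalence under a stated discordance rate.
- If an extension is kept, base it only on the standard deviation of IBS-SSS change and the overall discordance rate, with a target difference and a maximum size written down beforehand. Make the decision before any before-and-after comparison is tested, since a test at 120 followed by another later would still be two looks.
- Otherwise, declare the 120 a closed exploratory sample, reported as estimates with confidence intervals and used to plan a separate study whose data are not pooled with it for testing.

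The cost is one reworded paragraph, carried by an amendment. The real price is that a near-miss result can no longer trigger an extension.

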5.1 Pathogenesis & diagnosis of PCOS

Polycystic Ovarian Syndrome (PCOS) affects the endocrine system resulting in excessive androgen levels and the metabolic system which can lead to, for example, hyperinsulinemia. The disease is linked to a higher risk of preeclampsia, endometrial cancer, gestational diabetes and preterm birth. (3) Obesity, anovulation, polycystic ovaries and infertility can be seen in PCOS patients. (4) Due to these risks, women with PCOS are more likely to have to receive a fertility treatment to get pregnant and to prevent losing the pregnancy prematurely. PCOS affects up to 10% of women

(prevalence changes based on the use of different criteria). (5) The Rotterdam criteria are mostly used for diagnosis. Other diagnoses should be excluded and two out of three criteria need to be met. The three criteria are irregular cycles (criteria 1), high antimüllerian hormone or polycystic ovarian morphology on transvaginal ultrasound (criteria 2) and/or biochemical or clinical hyperandrogenism (criteria 3). (6)

5.2 Types of PCOS

There are four types of PCOS. Phenotype A PCOS has ovulatory dysfunction, hyperandrogenism and polycystic ovarian morphology. Phenotype B PCOS has the same characteristics but without the polycystic ovarian morphology. These two phenotypes are considered the “classic PCOS”. Phenotype C is characterized by hyperandrogenism and polycystic ovarian morphology. It is also called the ovulatory PCOS. Phenotype D PCOS is also called non hyperandrogenic PCOS, it is characterized by ovulatory dysfunction and polycystic ovarian morphology. (7)

5.3 Social freezing

The process of freezing your oocytes to preserve the ability to fertilize your own oocytes is called social (egg) freezing. The women receive ovarian stimulation (hormones) to grow as many follicles as possible before the pick-up of the oocytes. The oocytes are preserved using cryopreservation. The main reason for social freezing is the lack of an appropriate partner to start a family. (8)

5.4 Irritable bowel syndrome pathogenesis

The pathogenesis of irritable bowel syndrome has not been fully discovered. Patients experience gastro-intestinal motor problems and visceral hypersensitivity. IBS is associated with a modified gut microbiota which has an influence on immunity and the gut-brain axis. Genetic factors such as single nucleotide polymorphisms and epigenetic factors such as DNA methylation have been linked to IBS. (9) IBS patients are more likely to experience infertility. Most studies have focused on male infertility and IBS. A possible explanation for this link could be higher reactive oxygen species (ROS). However, more research is needed to explore this topic. (1) Serotonin dysregulation has been observed in patients with IBS. Patients with constipation showed a reduced level of serotonin concentrations and patients with diarrhea showed a higher level of serotonin concentrations. The serotonin concentration influences the secretion, sensation and motility of the gastrointestinal tract. More factors are possibly involved in the pathogenesis of IBS such as bacterial overgrowth, psychosocial factors, central dysregulation,... (10)

5.5 IBS and psychosocial factors

Patients with IBS have a higher risk of suffering from anxiety or depression, up to threefold higher than healthy subjects. (11) IBS symptoms exacerbate during stressful times. (12) A study investigated the stress levels during first and repeat IVF cycles and found higher stress levels in all IVF cycles. Women with lower stress levels had a higher pregnancy rate. Stress management can be beneficial for pregnancy rates and for IBS symptom severity. (13)

Studies about the relationship between depression and IBS are scarce and results are often inconsistent. Most studies find a higher rate of depression in IBS patients. The impact of depression on IBS symptom severity and prevalence hasn't been fully explored. Depression and IBS share a similar pathogenesis which makes it difficult to study these two diseases separately. Both IBS and depression show a dysfunction of the neuroendocrine systems and the immune system. (14)

5.6 IBS prevalence

The Rome Foundation Global study reported an overall prevalence of 3,8% when the Rome IV criteria are used and an overall prevalence of 10,1% when the Rome III criteria are used. (15) The Rome IV criteria question the prevalence of abdominal pain while the Rome III criteria additionally ask for abdominal discomfort (an uncomfortable sensation and not necessary pain). (16) Women have a significant higher prevalence of IBS than men, up to 3-fold higher. The risk of IBS doubles

when the person has a biological relative with IBS. The prevalence of IBS varies greatly between different countries. (17) PCOS patients are more prone to experience gastrointestinal (GI) disturbances such as irritable bowel syndrome (IBS): a recent meta-analysis showed that the risk of IBS in women with PCOS is two times higher than in a control group of women with no PCOS. (18) The prevalence of IBS during a fertility treatment has not been studied.

5.7 IBS subtypes

IBS has three subtypes. IBS-C has predominantly constipation, IBS-D has predominantly diarrhea and IBS-M is a mix of subtypes C and D. (19)

5.8 IBS symptoms during fertility treatments

Women can experience cramping, bloating and abdominal pain during the IVF cycles. After oocyte retrieval, diarrhea and constipation can occur. Most research about these symptoms have been focused on ovarian hyperstimulation syndrome (OHSS) and only few have tried to uncover how many women suffer from these symptoms outside of the OHSS context. (20)

This study will focus on the IBS symptoms experienced during fertility treatment. Some examples of drugs in fertility treatment include aromatase inhibitors, gonadotropin-releasing hormone (GnRH) and clomiphene. Aromatase inhibitors, for example letrozole inhibit the aromatization of androgen and thus reduces estrogen levels. This leads to increased GnRH release which results in more FSH production. (21) Aromatase inhibitors can cause headache, diarrhea and nausea. (22) GnRH-antagonists such as Cetrotide are used to prevent a premature rise of LH.(23) GnRH-agonists such as Decapeptyl are used for controlled ovarian hyperstimulation.(24) In a small study from 2015, severe dysmotility after taking GnRH analogs was linked to a high prevalence of endometriosis. Further research is needed, but it does hint at the possibility that patients with endometriosis have a higher chance of suffering from severe gastrointestinal symptoms. (25) Clomiphene citrate inhibits the negative feedback of estrogen to the pituitary and hypothalamus by binding estrogen receptors competitively. It stimulates the release of FSH which enhances follicle maturation. (26) Most common side effect of clomiphene are abdominal pain, diarrhea, anorexia and nausea. (27)

